7.5 Visit 5 – 6-month Follow-up

Visit 5 occurs 6 months (\pm 1 month) after the ablation procedure. The subject will visit the study site for the following assessments:

- Document any changes or updates to the subject's relevant concomitant medications (blood thinning/anticoagulants, antiplatelets, opioids, systemic chemotherapy, systemic

- steroids, immunotherapies, anti-inflammatories, NSAIDs, antibiotics, and medications used to treat adverse events)
- Document any changes or updates to the subject's concomitant procedures.
- Complete two validated quality of life questionnaires: EORTC QLQ-C30 and the lung-specific QLQ-LC13. These questionnaires should be administered in person, during the study visit. However, they may be administered over the phone, when needed.
- Collect key vitals: blood pressure, heart rate, and pulse oximetry.
- Evaluate ECOG performance status.
- Obtain PFTs, which include Spirometry (e.g., FEV1, FVC, FEV1/FVC, FEF25-75, Peak Expiratory Flow, and Maximum Ventilation Volume), Diffusion Capacity (DLCO), Total Lung Capacity (TLC), Functional Residual Capacity (FRC), and Residual Volume (RV).
- Complete chest CT, abdomen and pelvis CT, brain MRI (if site SOC), and extremity CT or MRI (if site SOC) to determine Tumor Progression. Contrast-enhanced images are preferred but not required. If a site takes a PET scan per SOC, the other images should also be taken, per protocol:
 - Local Tumor Progression (LTP), defined as recurrence of the originally ablated tumor(s) within or abutting the ablation zone using Chest CT and the 30-day post-ablation imaging as the baseline.
 - Regional Tumor Progression includes new or progression of pre-existing tumors that were not previously ablated within either lung using chest CT.
 - Distant Tumor Progression includes new or progression of pre-existing tumors outside of the lung using abdomen and pelvis CT, brain MRI, and extremity CT or MRI.
- Record any applicable AEs or SAEs:
 - Record any AEs or SAEs that may have occurred within 30 days of an ablation or re-ablation procedure.
 - Record only device- or procedure-related AEs or any SAEs that may have occurred after 30 days of an ablation or re-ablation procedure.

7.6 Visit 6 – 12-month Follow-up

Visit 6 occurs 12 months (\pm 1 month) after the first ablation procedure. The subject will visit the study site for the following assessments:

- Document any changes or updates to the subject's relevant concomitant medications (blood thinning/anticoagulants, antiplatelets, opioids, systemic chemotherapy, systemic steroids, immunotherapies, anti-inflammatories, NSAIDs, antibiotics, and medications used to treat adverse events)
- Document any changes or updates to the subject's concomitant procedures.
- Complete two validated quality of life questionnaires: EORTC QLQ-C30 and the lung-specific QLQ-LC13. These questionnaires should be administered in person, during the study visit. However, they may be administered over the phone, when needed.
- Collect key vitals: blood pressure, heart rate, and pulse oximetry.
- Evaluate ECOG performance status.

- Obtain PFTs, which include Spirometry (e.g., FEV1, FVC, FEV1/FVC, FEF25-75, Peak Expiratory Flow, and Maximum Ventilation Volume), Diffusion Capacity (DLCO), Total Lung Capacity (TLC), Functional Residual Capacity (FRC), and Residual Volume (RV).
- Complete chest CT, abdomen and pelvis CT, brain MRI (if site SOC), and extremity CT or MRI (if site SOC) to determine Tumor Progression. Contrast-enhanced images are preferred but not required. If a site takes a PET scan per SOC, the other images should also be taken, per protocol:
 - Local Tumor Progression (LTP), defined as recurrence of the originally ablated tumor(s) within or abutting the ablation zone using Chest CT and the 30-day post-ablation imaging as the baseline.
 - Regional Tumor Progression includes new or progression of pre-existing tumors that were not previously ablated within either lung using chest CT.
 - Distant Tumor Progression includes new or progression of pre-existing tumors outside of the lung using abdomen and pelvis CT, brain MRI, and extremity CT or MRI.
- Record any applicable AEs or SAEs:
 - Record any AEs or SAEs that may have occurred within 30 days of an ablation or re-ablation procedure.
 - Record only device- or procedure-related AEs or any SAEs that may have occurred after 30 days of an ablation or re-ablation procedure.

7.7 Unscheduled Visits

The following data will be collected during each unscheduled visit:

- Reason for the unscheduled visit.
- Document any changes or updates to the subject's relevant concomitant medications (blood thinning/anticoagulants, antiplatelets, opioids, systemic chemotherapy, systemic steroids, immunotherapies, anti-inflammatories, NSAIDs, antibiotics, and medications used to treat adverse events)
- Document any changes or updates to the subject's concomitant procedures.
- Record any applicable AEs or SAEs:
 - Record any AEs or SAEs that may have occurred within 30 days of an ablation or re-ablation procedure.
 - Record only device- or procedure-related AEs or any SAEs that may have occurred after 30 days of an ablation or re-ablation procedure.

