	
Technical Success, Repeat Ablation Efficacy, and Hospital Readmission Rate will be summarized in a similar manner. Local Tumor Progression, Local Tumor Progression Free Survival, Progression Free Survival, and Overall Survival will be estimated using the Kaplan-Meier method and confidence intervals will be provided.
 
The number and percentage of subjects experiencing device-related AEs will be summarized by the MedDRA system organ class and preferred term. A similar summary will also be provided for procedure-related AEs and all SAEs.
 
Summary statistics will be provided for all other endpoints as defined within the protocol.

Interim Analyses	
The first interim analysis will occur after 20 subjects complete Visit 3 (30 days) and will be descriptive in nature only and will not impact the final analysis.
 
The second interim analysis will occur after all subjects complete Visit 3 (30 days) and will include an evaluation of the primary endpoint against the performance goal as well as provide a summary of all baseline and procedural-related data. A complete summary of all safety-related data observed through the duration of follow-up on all subjects will also be provided. The intent of this analysis will be to support regulatory filing activities where appropriate.
 
An additional interim analysis may be performed after all subjects have completed Visit 5 (6 months).
 
The final analysis will be completed once all subjects have completed Visit 6 (12 months) and will summarize all endpoints collected during the trial.

Time and Events Schedule	See Table 1 on the next page.

Table 1: Schedule of Assessments

Visit No.	Visit 1	Visit 2			Visit 3	Visit 4	Visit 5	Visit 6	Unsched. Visit ²¹
Visit	Screening	Pre-Procedure	Intra-Procedure	Post-Procedure	Follow-up	Follow-up	Follow-up	Follow-up	
Interval Windows	≤ 30 days pre-ablation	Day 0	Day 0	Day 0 - Discharge	30 days (-7 to +14 days)	3 months (±2 weeks)	6 months (±1 month)	12 months (±1 month)	
Standard Study Assessments									
Informed Consent	X								
Inclusion / Exclusion Criteria	X	X							
Demographics	X								
Medical / Surgical History ¹	X								
Concomitant medications ²	X	X		X	X	X	X	X	X
Concomitant procedures	X	X		X	X	X	X	X	X
BMI	X								
Key Vitals ³	X	X		X	X	X	X	X	
ECOG Status	X	X			X	X	X	X	
Pulmonary function tests (PFTs)	X					X	X	X	
Laboratory Assessments									
Pregnancy test ⁴	X	X							
Coagulation tests ⁵	X	X ⁶							
CBC with differential	X								

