16. Measure and record the size of the tumor(s) on the day of ablation using CBCT. Afterwards, use cone beam CT to guide the microwave ablation probe to the target tumor(s) and ascertain the location of the probe after the robotic bronchoscope has been retracted. CBCT scans will be used at a minimum of three timepoints pre- and post- the ablation process: (1) Pre-Navigation: Prior to starting navigation, CBCT will be used to establish baseline imaging, confirm tumor details, and tumor segmentation for navigation (i.e., augmented fluoroscopy), (2) Pre-Ablation: Immediately before the ablation, use CBCT to confirm that the probe is in the intended location, and if it is not, reposition the probe, and (3) Post-Ablation: After completing the ablation, use CBCT to confirm that the ablation margins are adequate. Note: Technical Success will be determined based on CBCT image analysis.
17. Perioperative AEs will be captured from the time of subject consent through 30-days post any ablation procedure (i.e., the original ablation as well as any re-ablation) regardless of relationship to the study device or procedure. AEs that are deemed related to the study device or procedure will

be captured 30-days post any ablation procedure (i.e., the original ablation as well as any re-ablation) through the end of the study or early termination. SAEs will be captured from the time of subject consent through the end of the study or early discontinuation regardless of relationship to the study device or procedure.

18. UB-04 data collection is applicable for US sites only.
19. Length of hospital stay (LOS), measured from post-ablation to discharge. After the ablation procedure, the subject will be observed for up to 23 hours before discharge, except in cases where the Investigator deems it is necessary for the subject to remain hospitalized.
20. Record readmission to any hospital for any unplanned reason within 30 days of any ablation procedure (i.e., the original ablation as well as any re-ablation). The Investigator will assess the reason for the admission and capture the reason in the clinical database.
21. Record reason for unscheduled visit, as well as AEs (if applicable), and any updates to concomitant medications, concomitant procedures, or any other study assessments, per site SOC.

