4.5 Central Review Committee

A central review committee of radiologists will independently review all CT scans (and other scans, as applicable) taken throughout the clinical study in an effort to standardize scan assessment and to minimize potential bias of the treating physician. Both the clinical site's radiographic assessment and the central review committee's assessment will be captured within the CRFs and reported within the final Clinical Study Report. The central review assessment for the following key endpoints will be used for the final analysis. The central review committee will analyze uploaded subject images from the site to assess the following key endpoints and data:

Assessment	Visit 1 (Screening)	Visit 2 (Ablation Visit)	Visit 3 (30 days post-ablation)	Visit 4 (3 months post-ablation)	Visit 5 (6 months post-ablation)	Visit 6 (12 months post-ablation)
Tumor size* (smallest and largest diameters)	X					
Ablation zone (smallest and largest diameters)		X				
Smallest minimal ablation margin		X				
Technical Success		X				
Technique Efficacy			X			
Local tumor progression				X	X	X
Other tumor progression (regional or distant)				X	X	X

*Tumor size, as analyzed by the central review committee, will be used for reporting purposes only. The investigator's assessment of tumor size will be used for inclusion/exclusion purposes.

The composition of the committee and details of how the endpoints will be defined will be specified in a separate Imaging Charter, which will be finalized prior to enrolling the first subject.

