All applicable scans (i.e., cone beam CT scans (taken during the ablation procedure), all conventional CT scans (taken during the post-ablation follow-up visits), and applicable PET scans should be de-identified and uploaded to the study imaging database in DICOM (digital imaging and communications in medicine) format, if possible. The imaging database will be controlled and maintained by the same vendor that organized and contracted the Central Review Committee, [REDACTED]

[REDACTED] The Sponsor will have "read-only" access to the imaging database during the study. Separate instructions for the site to de-identify and upload all applicable scans will be provided in a separate document.

Also, only for those subjects who specifically consent, some ablation procedures may be filmed for training and educational purposes.

Source documents must be retained by the Investigator as part of the subject's permanent medical record. The information in the source documents is used to complete the eCRFs. All

information captured on the eCRFs should be completely and accurately supported in source documentation. Any additional information relevant to the study should be included in the source documents. Particularly, any deviations from the protocol or procedures should be recorded in the source documents. The Investigator will retain originals of all source documents, subject consent forms, and study data.

Electronic Data Capture

An EDC system will be used by site personnel to transfer data from source records (medical records and/or source document worksheets) onto common eCRFs. This system is a web-based, secure electronic software application [REDACTED] [REDACTED] [REDACTED]

[REDACTED]. This system was designed and is developed and maintained by [REDACTED] in a manner that is compliant with national and international GCP data protection/data privacy and electronic record/electronic signature (e.g., 21 CFR Part 11) regulatory requirements. The EDC system will be used to facilitate the collection of all data at the site. Designated site personnel will be responsible for entering subject data into the EDC system. All external and Sponsor internal users will be trained on the EDC application at a level dependent on their planned function. An EDC digital User Manual will be available under the help menu within the [REDACTED] website to assist in the collection and entry of source data into the electronic casebook.

A 24/7/365 Help Desk Support line [REDACTED]

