**Time to Event Endpoints:**

Local Tumor Progression Free Survival (LTPFS) is defined as: Time from the ablation until local tumor(s) progression (LTP) or death, whichever occurs first.

Progression Free Survival (PFS) is defined as: Time from the original ablation until tumor(s) progression or death, whichever occurs first (includes local, regional, or distant progression). Specifically: For local tumors, time from the original ablation until tumor(s) progression or death, whichever occurs first. For regional and distant tumors, time from study day 0 or last local therapy (if treated after study initiation) until tumor(s) progression or death, whichever occurs first.

Disease (cancer) Specific Survival (DSS) is defined as: Time from the original ablation until death from the treated primary malignancy.

Overall Survival (OS) is defined as: Time from the original ablation until subject death (includes death from any cause).

Local Tumor Progression Free Survival (LTPFS), Progression Free Survival (PFS), Disease Specific Survival (DSS), and Overall Survival (OS) will be estimated using the Kaplan-Meier method with 95% confidence intervals provided at month 12. The time from the day of the initiation ablation procedure to the specific event will be derived.

Patients who are re-ablated are considered as reaching an event respectively for each of the LTP, LTPFS and PFS event definitions.

Patients without a progression event, as defined above, will be censored by the last contact date (the last date in the study).

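### The plan has no consistent rule for capturing, centrally reading and dating progression found between scheduled visits, so PFS and LTPFS may be overstated

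*Protocol*

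**What the plan says.** **Passages that confine progression to scheduled visits.**
- Protocol 7.7 opens with "The following data will be collected during each unscheduled visit" and lists the reason for the visit, medications, procedures and adverse events.
- The imaging instruction "Complete chest CT, abdomen and pelvis CT, brain MRI (if site SOC), and extremity CT or MRI (if site SOC) to determine Tumor Progression" appears under Visit 5, and in the same terms under Visits 4 and 6. The Tumor Progression row of Table 1 has no mark in the Unscheduled column.
- The assessment tables in Protocol 4.5 and SAP 1 place local, regional and distant progression at Visits 4, 5 and 6 only.
- Protocol 8.1 describes the follow-up images for upload as "all conventional CT scans (taken during the post-ablation follow-up visits"). It does not name scans taken at other times.

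**Passages that point the other way.**
- Table 1 note 21, attached to the Unscheduled column, asks for "any updates to concomitant medications, concomitant procedures, or any other study assessments, per site SOC".
- Protocol 4.5 opens by saying that the central committee "will independently review all CT scans (and other scans, as applicable) taken throughout the clinical study".

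**Analysis rules.** SAP 8.10 makes the central reading the primary result for local and other progression. SAP 8.8.2 counts death and re-ablation as events for PFS and LTPFS, reports Kaplan-Meier estimates at month 12, and states: "Patients without a progression event, as defined above, will be censored by the last contact date (the last date in the study"). It does not say which date an event takes when progression is first seen between visits.

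**The concern.** A scan taken between visits is often taken because progression is suspected. The longest interval without a scheduled scan lies between Visits 5 and 6. A site that follows 7.7 and the tables has no instruction to upload such a scan or to have it read for progression. Two things can then happen.

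1. **Late dating.** The progression is first read at Visit 6 and dated there.
2. **Loss.** The progression is never counted. Protocol 5.5 leaves surgery, radiotherapy and systemic therapy to clinical discretion once the restriction period ends, and SAP 8.8.2 treats only re-ablation as an event. If the lesion is treated in another way, or the subject leaves, before Visit 6, the subject can be censored as progression-free at last contact. A new lung tumor ablated as non-target (Protocol 6.1) is a related case. Protocol 7.6 limits regional progression to tumors not previously ablated, so by Visit 6 that tumor arguably no longer qualifies.

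Month-12 LTPFS and PFS are two of the four secondary endpoints that SAP 5 singles out for confidence intervals after primary success. Protocol 3.0 quotes one-year PFS for existing options, which invites comparison.

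**Working it through.** **The plan's own figures.** The only design calculation is for Technique Efficacy. It reproduces: n = [(1.960 × √(0.8 × 0.2) + 1.2816 × √(0.9 × 0.1)) / 0.10]² = 136.5, so 137, and 137 / 0.95 = 144.2, so 145. PFS and LTPFS have no calculation in the plan, so what follows is illustration.

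**Length of the gap.** Visit 5 falls in months 5 to 7 and Visit 6 in months 11 to 13. The nominal gap is 6 months, with a range of 11 − 7 = 4 to 13 − 5 = 8.

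**Events in the gap.** The input is one-year PFS of 58% (95% CI 49% to 67%) for image-guided ablation, from Protocol 3.0. A constant hazard is assumed, and every event is taken as progression. Deaths are dated exactly, so this gives an upper bound.
- Hazard = −ln(0.58) / 12 = 0.0454 per month.
- S(6) = √0.58 = 0.762.
- S(6) − S(12) = 0.182, and 0.1816 × 145 = 26.3 subjects.
- At the interval's ends: (0.700 − 0.490) × 145 ≈ 30, and (0.8185 − 0.670) × 145 ≈ 21.5.

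**Late dating, nobody lost.** This was simulated with 300,000 subjects, scan times uniform within their windows, and subjects without an event censored at Visit 6. The LTPFS column assumes 85% at 12 months. Protocol 3.0 gives local control above 85% without a time point.

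| Visit 6 timing | Month-12 PFS, dated at scheduled scans | True dates | LTPFS, dated at scheduled scans | True dates |
|---|---|---|---|---|
| Exactly month 12 | 57.8% | 57.8% | 85.1% | 85.1% |
| Uniform, months 11–13 | 65.1% | 57.8% | 87.8% | 85.1% |
| Always months 12–13 | 76.0% | 57.8% | 92.2% | 85.1% |

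Between visits the curve is too high in each case: at month 9 it reads 76.0% against 66.3%. Events dated at month 12 instead of when they occur are delayed by 3.1 months on average. In the second row, counting half of the Visit 5–6 progressions at an unscheduled scan lowers 65.1% to 61.3%. If every Visit 6 fell before month 12, the estimate became unstable and too low, because censoring at Visit 6 empties the risk set.

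**Loss through censoring.** Take Visit 5 at month 6 and Visit 6 at month 12, and let a fraction u of the progressors in between be censored. The month-12 estimate becomes S(6) × S(12) / [S(6) − u × (S(6) − S(12))].
- u = 10%: 0.4417 / 0.7434 = 59.4%
- u = 25%: 0.4417 / 0.7162 = 61.7%
- u = 50%: 0.4417 / 0.6708 = 65.9%

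The simulation, with the Visit 5 window included, gave 59.2%, 61.5% and 65.6% against 57.8%. The documents supply no value for u.

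**The case against.** A reader might infer that unscheduled visits record no progression, that progression found between visits is never counted, and that PFS and LTPFS are therefore overstated as a matter of fact. The documents do not support that.

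- **Recording.** Section 7.7 does not say that its list is exhaustive. Note 21 and the opening of 4.5 both allow unscheduled scans to be recorded and reviewed.
- **Counting.** Death and re-ablation are events, and progression still visible at Visit 6 is read there. Other local treatment is recorded as a concomitant procedure, and SAP 8.6 summarizes procedures by indication, including disease progression.
- **Dating.** No rule moves an event to a visit date. The SAP is silent; it does not prescribe late dating.
- **Unseen documents.** The Imaging Charter and the upload instructions may settle some of this.
- **Bias.** Late dating does not bias the month-12 estimate if Visit 6 is at month 12, and the direction there is not fixed. Some late dating comes with any fixed imaging schedule.
- **Importance.** PFS and LTPFS are not tested. A shift of 2 to 5 points lies within the sampling error of 58% in 145 subjects: 1.96 × √(0.58 × 0.42 / 145) ≈ 8 points.

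All of this stands against the stronger reading. It does not close the gap. Note 21 depends on site practice and sets no reading or dating rule. The committee works from images that the site uploads, and 8.1 does not name unscheduled scans. Since the central reading is primary, a site entry alone would not settle the result. A procedure listing is not an event rule, and Protocol 12.1 keeps progression out of SAE reporting. Sampling error also does not excuse a systematic error that wording can prevent.

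**Conclusion.** The concern holds as a conflict between passages and a missing rule. Section 7.7 and the tables limit progression to Visits 4, 5 and 6, while note 21 and the text of 4.5 imply more. The SAP neither dates progression found between visits nor censors at the last evaluable scan. The result may be an overstatement of PFS and LTPFS; it is not a demonstrated one.

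The curve between visits is too high wherever events are dated late. The month-12 estimate is affected when Visit 6 falls after month 12 or when progressors are censored. Under the stated assumptions, censoring 10% to 50% of the Visit 5–6 progressors adds roughly 1.5 to 8 points to a month-12 PFS of 58%. The late-dating figures in the table reflect the visit schedule as a whole, so only the part found on unscheduled scans can be recovered. The 30-day primary endpoint and its sample size are unaffected. This is a worthwhile, inexpensive correction to secondary endpoints.

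**What to change.** - **Protocol 7.7, the Table 1 Unscheduled column, and the tables in 4.5 and SAP 1:** align them with note 21. Any chest, abdomen/pelvis, brain or extremity scan done outside a scheduled visit is uploaded and assessed for local, regional and distant progression by the site and the existing central committee. The upload wording in 8.1 should match.
- **SAP 8.8.2:** date the PFS or LTPFS event at the first scan showing progression, scheduled or not. Censor subjects without an event at the last evaluable scan instead of at last contact.

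Ordinary interval censoring between scans will remain. An interval-censored sensitivity analysis could show its size.

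**Cost.** Wording changes to the protocol and SAP, and a limited number of extra central reads. No additional scans are needed. The PFS estimate may come out slightly less favourable.
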